***Statistical analyses***

General considerations: Statistical procedures and models for analyzing data have been selected according to the research hypotheses being investigated and the types of data available. In general, p-values <0.05 will be considered statistically significant. When necessary, however, we will use appropriate corrections of p-values to account for multiple statistical tests. Statistical analyses will be conducted on an intention-to-treat sample using SAS Release 8.1 (SAS Institute, Inc., Cary, NC) and SPSS 14.0 (SPSS Inc., Chicago IL) statistical packages. Where appropriate, hypotheses will be tested by independent statistical analyses using Mixed Models procedure to test for significant effect of group assignment (VIVITROL vs. placebo), time, and the interaction between group assignment and time. Loss to follow-up is of concern in longitudinal analyses, particularly if loss to follow-up is differential. We plan to use established strategies (> 90% follow-up) to reduce loss to follow-up [122, 124]. A benefit of the mixed effects models approach is that subjects who do not have complete information on the outcome variable can be included, provided that missing data is missing at random.

**Specific Aim 1:** To compare the efficacy of VIVITROL +MM/MC versus placebo +MM/MC on adherence to HAART.

**Hypothesis 1:** VIVITROL +MM/MC will lead to improved adherence to HAART when compared to placebo + MM/MC.

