There are multiple strategies to measure adherence (See Sections B.8. and B.9.). Based on strong evidence in support of this strategy [72, 88, 89], we have chosen to examine the percentage of patients, using pharmacy fill-refill data, who achieve 95% or better adherence to their HAART treatment as our primary outcome measure of adherence [60, 117]. We will also examine adherence using self-report data collected using AIDS Clinical Trials Group (ACTG) assessment. Patients will be classified as meeting the criteria for greater than 95% adherence if they are adherent 29-30 days out of the past 30 days. We will use the Chi-Square test to compare the proportion of patients in each randomization group meeting these criteria during each month of the study. The t-test will be used to compare HAART medication adherence between the two treatment conditions based on self-report.

**Specific Aim 2:** To compare the efficacy of VIVITROL +MM/MC versus placebo +MM/MC in reducing days of heavy drinking.

**Hypothesis 2:** VIVITROL +MM/MC counseling will lead to greater reductions in the number of days of heavy drinking when compared to placebo + MM/MC.

We plan to use a standard alcohol consumption outcome, the number of days of heavy drinking (4 or more drinks per drinking occasion for women and 5 or more drinks per drinking occasion for men) in the past 30 days. This measurement was one of the outcomes

APPROVED BY THE YALE UNIVERSITY IRB 10/11/2018 VALID THROUGH 10/13/2019  

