that differed between the control and VIVITROL group in the recent study of extended release VIVITROL [57]. The planned analyses for this outcome will include examining the number of days of heavy drinking over the 24-week treatment period and at the 9-month and 12-month follow-up periods. This measure will be based on self-reported alcohol use from the Time-Line Follow Back. Since individuals may choose to leave during treatment and a small proportion could be lost to follow-up we plan to use repeated measures analysis of variance with the MIXED Models procedure. The MIXED Models procedure was designed for unbalanced repeated measures with missing data, allowing for intra-participant serial correlation and unequal variance and covariance structure across time [137]. A repeated measures analysis of variance in the Mixed Models procedure takes into consideration differences that may emerge over time, and we will use this procedure to test for a significant treatment effect, time effects, and the interaction of these two on the primary outcome measure.

**Specific Aim 3 (Exploratory):** To explore the effect of VIVITROL +MM/MC versus placebo +MM/MC on biologic outcomes including:  
3a) HIV markers—viral mutations (using standard assays and ultra-deep sequencing), CD4 lymphocyte count and HIV RNA level; and  
3b) Liver function tests

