**Specific Aim 3a:**

To compare differences between the two treatment conditions in the impact on viral mutations, we will use descriptive statistics to report the prevalence of current HIV drug resistance mutation patterns at baseline and at 24-weeks, 9 and 12 months. HIV resistance mutations, as defined by the International AIDS Society guidelines [138], will be evaluated. We will evaluate the association between heavy drinking and HIV viral mutations first in a dichotomous way. We will evaluate the bivariate association of heavy drinking and viral mutations and conduct a chi-square evaluation that contrasts the development of HIV viral mutations (positive vs. negative) with heavy drinking (yes vs. no). Subsequently we will conduct exploratory analyses using multinomial logistic regression to adjust for the potential effects of prior resistance mutations, antiretroviral medication class, duration of HIV disease, and duration of HAART. We will explore the effect of HAART adherence on the relationship between heavy drinking and the development of HIV drug resistance using sequential modeling to test for a potential mediating effect of HAART adherence. Finally, we will conduct an exploratory analysis to determine if the presence and quantity of minor variants affects virologic and HIV outcomes.

To compare differences between the treatment conditions, monthly CD4 lymphocyte counts and HIV RNA will be evaluated using the Mixed Models repeated-measures analysis controlling for baseline differences. To compare differences between the treatment conditions on their impact on liver function tests and Fib-4, we will use the Mixed Models repeated-measures analysis controlling for baseline differences.

We also plan to explore the effect of the treatment conditions on sexual risk behaviors (as measured by the HRBS on a monthly basis). A Mixed Models repeated-measures analysis will be used to evaluate treatment group, time, and interaction effects. We will also collect data on baseline hepatitis status, depressive symptoms at baseline and at the completion of the study, and any side effects reported by patients during the course of the study.

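### Aim 2 names no deciding test for heavy drinking, and its stated model includes neither baseline drinking nor the randomisation strata

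*Combined protocol and SAP*

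**What the plan says.** Hypothesis 2 (Section V, Statistical analyses, Specific Aim 2) is that active treatment "will lead to greater reductions in the number of days of heavy drinking when compared to placebo". The outcome is the number of heavy-drinking days in a 30-day window, taken from the Time-Line Follow Back (TLFB). The planned analyses include "examining the number of days of heavy drinking over the 24-week treatment period and at the 9-month and 12-month follow-up periods". The method is repeated-measures analysis of variance in a mixed model, used to "test for a significant treatment effect, time effects, and the interaction of these two" on what the text calls the primary outcome measure. In that paragraph this term can only sensibly mean the Aim 2 outcome, because the Assessments overview lists heavy drinking first among the secondary outcomes.

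The General considerations name the same three terms for mixed models across the trial. They state "In general, p-values <0.05 will be considered statistically significant", and add that, when necessary, "we will use appropriate corrections of p-values to account for multiple statistical tests". No method, family of tests or trigger is given, and Aim 2 is not mentioned.

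Two prognostic inputs are available before treatment. The Alcohol Use entry has the TLFB cover the month before baseline, and Table 1 schedules it at week -1. The Randomization paragraph defines six strata: three clinics by alcohol abuse/dependence (yes/no). The Aim 2 model mentions neither. In Specific Aim 3a, by contrast, CD4 count, HIV RNA, liver tests and FIB-4 are analysed "using the Mixed Models repeated-measures analysis controlling for baseline differences".

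**The concern.** The treatment effect and the treatment-by-time interaction answer different questions. With post-baseline visits only, a benefit that appears in month 1 and stays constant lies wholly in the treatment effect and not at all in the interaction. A benefit that builds up shows in both. With baseline as the first repeated level, the interaction carries the change from baseline, and the averaged treatment effect includes a visit at which no drug effect can exist. A reader of the final report could not tell from the plan which p-value was meant to decide Hypothesis 2, nor whether the 24-week period or the follow-up visits were meant to count.

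Silence on baseline makes this worse. Hypothesis 2 concerns reduction, but an unadjusted post-baseline treatment effect compares levels. It also carries between-person variation in drinking that the baseline TLFB and the strata could remove. The documents give no power figure for Aim 2, so any precision available without new data is worth having.

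**Working it through.** **The plan's own figure.** The only design figure is 72% power for Aim 1 (Sample size estimation: 20% versus 40%, 154 participants, alpha 0.05). Taking 77 per arm, the continuity-corrected two-proportion formula gives 72.1%, so it reproduces. It does not bear on Aim 2, for which the documents give no effect size, standard deviation, correlation or power.

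**Step 1: false-positive rate if either test may confirm Hypothesis 2.** Inputs: 0.05 per test (General considerations; two-sided assumed), 77 per arm, and six four-week periods in 24 weeks.

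- Independent tests: 1 − 0.95² = 9.75%.
- Correlated tests (bivariate normal): 9.1% at correlation 0.5 and 7.0% at 0.9.
- Null simulations, 6,000 trials per setting, errors either compound symmetric (0.5) or AR(1) (0.7), with baseline unused, as a level or as a covariate: 9.2% to 10.0% for the averaged treatment effect or the interaction. Simulation error is about 0.4 percentage points, since √(0.095 × 0.905 / 6,000) = 0.0038, so the top of this range is not distinguishable from 9.75%.
- Same simulations, with the treatment effect coded as the group difference at the first time point: 8.0% to 9.5%, because that coefficient is correlated with the interaction.
- One pre-named contrast at 0.05: 5%. Both tests kept at 0.025 each: 1 − 0.975² = 4.9%.

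**Step 2: dilution if baseline is a repeated level.** Assume a constant effect δ at every post-baseline visit, none at baseline, and equal weights.

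- Baseline plus six treatment months: (0 + 6δ)/7 = 6δ/7, or 0.857δ.
- Adding months 9 and 12: (0 + 8δ)/9 = 8δ/9, or 0.889δ. This assumes that the effect persists, which the Study Period paragraph itself doubts. With no effect at those two visits the average is 6δ/9, or 0.667δ.

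This is shrinkage of the estimate. What it does to power depends on correlations that the documents do not give.

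**Step 3: precision from baseline adjustment.** Let r be the assumed correlation between baseline and any one visit, with unit variances.

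- Single visit: the variance is multiplied by 1 − r².
- Mean of T visits under compound symmetry: unadjusted variance V = [1 + (T − 1)r]/T, adjusted variance V − r², reduction r²/V.

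| Assumed r | Single-visit reduction | V (T = 6) | V − r² | Reduction for six-visit mean |
|---|---|---|---|---|
| 0.3 | 9% | 0.417 | 0.327 | 22% |
| 0.5 | 25% | 0.583 | 0.333 | 43% |
| 0.7 | 49% | 0.750 | 0.260 | 65% |

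The six-visit column matches a contrast averaged over the treatment period. The gain from adding the strata cannot be computed from the documents.

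**The case against.** Three stronger readings are tempting, and the documents support none of them.

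- **That Aim 2 has a false-positive rate of about 10%.** The plan lists terms to be tested. It never says that either one suffices, and the General considerations promise corrections when necessary. The rate is conditional on an uncorrected either-test rule that the plan leaves open. Nor does the plan say that months 9 and 12 will be tested as further separate chances of success.
- **That baseline drinking is left out and its information wasted.** The text is silent on how baseline enters. A hypothesis about reductions, tested in a repeated-measures model with time and interaction, is compatible with baseline as the first level. Its information would then be used, and the interaction would be the natural test; the dilution in Step 2 would matter little if the interaction were named as decisive. The contrast with Aim 3 is also incomplete: the sexual-risk analysis in the same section lists treatment, time and interaction with no mention of baseline. The missing phrase points to under-specification, not to a decision against baseline.
- **That a definite number of participants' worth of precision is lost.** No baseline correlation is given, so only a range under assumptions can be shown.

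It is also fair to say that the choice of contrast is open. A 24-week average, a change from baseline and an interaction are all defensible, and the Aim 2 text does stress differences that emerge over time.

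What remains is that no term or period is named as decisive, the correction clause supplies neither a method nor a family, and the model as stated lacks two covariates that the trial already holds.

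**Conclusion.** The point holds as one of specification and efficiency. Aim 2 names no deciding contrast or period for Hypothesis 2, and its stated model includes neither baseline heavy-drinking days nor the strata. If either test were accepted at 0.05 uncorrected, the false-positive rate would be about 8% to 10%, depending on how the treatment effect is coded. If baseline is a repeated level, the averaged treatment effect is diluted to 6/7, or to 8/9 when months 9 and 12 are also levels with a persisting effect, and only the interaction tests reduction. The precision gain from adjustment is 9% to 49% of variance for a single visit and about 22% to 65% for a six-visit mean. Those figures rest on assumed correlations of 0.3 to 0.7 and, for the mean, on compound symmetry. Heavy drinking is a secondary outcome, so the primary adherence conclusion is unaffected; the change should be made but is not critical to the trial.

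**What to change.** Name one contrast for Hypothesis 2 in the SAP. A suitable choice is the XR-NTX minus placebo difference in mean monthly heavy-drinking days over the 24-week treatment period. Estimate it from the mixed model with post-baseline months as outcomes, and with baseline TLFB heavy-drinking days, clinic and alcohol abuse/dependence as covariates. Test it at 0.05, and report the treatment-by-time interaction and the month 9 and month 12 differences as supportive.

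If the team prefers the interaction or a change from baseline, that can be named instead, provided that it is the only deciding test and the role of baseline is stated. If two deciding tests are wanted, state the correction, for example 0.025 each.

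The cost is a few sentences of SAP wording, settled before unblinded outcome data are examined. No new data, visits or participants are needed.

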**Specific Aim 3a:**

To compare differences between the two treatment conditions in the impact on viral mutations, we will use descriptive statistics to report the prevalence of current HIV drug resistance mutation patterns at baseline and at 24-weeks, 9 and 12 months. HIV resistance mutations, as defined by the International AIDS Society guidelines [138], will be evaluated. We will evaluate the association between heavy drinking and HIV viral mutations first in a dichotomous way. We will evaluate the bivariate association of heavy drinking and viral mutations and conduct a chi-square evaluation that contrasts the development of HIV viral mutations (positive vs. negative) with heavy drinking (yes vs. no). Subsequently we will conduct exploratory analyses using multinomial logistic regression to adjust for the potential effects of prior resistance mutations, antiretroviral medication class, duration of HIV disease, and duration of HAART. We will explore the effect of HAART adherence on the relationship between heavy drinking and the development of HIV drug resistance using sequential modeling to test for a potential mediating effect of HAART adherence. Finally, we will conduct an exploratory analysis to determine if the presence and quantity of minor variants affects virologic and HIV outcomes.

To compare differences between the treatment conditions, monthly CD4 lymphocyte counts and HIV RNA will be evaluated using the Mixed Models repeated-measures analysis controlling for baseline differences. To compare differences between the treatment conditions on their impact on liver function tests and Fib-4, we will use the Mixed Models repeated-measures analysis controlling for baseline differences.

We also plan to explore the effect of the treatment conditions on sexual risk behaviors (as measured by the HRBS on a monthly basis). A Mixed Models repeated-measures analysis will be used to evaluate treatment group, time, and interaction effects. We will also collect data on baseline hepatitis status, depressive symptoms at baseline and at the completion of the study, and any side effects reported by patients during the course of the study.

**SECTION VI: RESEARCH INVOLVING DRUGS, DEVICES, BIOLOGICS & PLACEBOS**

1. **Identification of Drug, Device or Biologic:** What is (are) the **name(s)** of the drug(s), device(s) or

biologic(s) being used? Identify whether FDA approval has been granted and for what indication(s).

Extended release formulation of naltrexone (XR-NTX; Vivitrol®).

All protocols which utilize a drug, device or biologic **not** approved by, but regulated by, the FDA must provide the following information:  **Not applicable to this research project**

- i. What is the Investigational New Drug (IND) or Investigational Device Exemption (IDE) **number** assigned by the FDA?
- ii. For IDE's: Did the FDA approve this IDE as a Category A (experimental/investigational) or as a Category B (non-experimental/investigational)?
- iii. Who holds the IND or IDE?

The clinical investigation of a drug product that is lawfully marketed in the United States may be exempt from the requirements for filing an IND. If there is no IND and an exemption is being sought, complete the following: NA

- i. Is the intention of the investigation to report to the FDA as a well controlled study in support of a new indication for use or to be used to support any other significant change in the labeling for the drug?  Yes  No
1. If the drug that is undergoing investigation is lawfully marketed as a prescription drug product, is the intention of the investigation to support a significant change in the advertising for the product?  Yes  No
- iii. Does the investigation involve a route of administration or dosage level or use in populations or other factor that significantly increases the risks (or decreases the acceptability of the risks) associated with the use of the drug product?  Yes  No
1. Will the investigation be conducted in compliance with the requirements for institutional (HIC) review and with the requirements for informed consent of the FDA regulations (21 CFR Part 50 and 21 CFR Part 56)?  Yes  No
- v. Will the investigation be conducted in compliance with the requirements regarding promotion and charging for investigational drugs?  Yes  No
2. **Background Information:** Provide a description of previous human use, known risks, and data addressing dosage(s), interval(s), route(s) of administration, and any other factors that might influence risks. If this is the first time this drug is being administered to humans, include relevant data on animal models.

Numerous studies have found NTX to be safe and rarely associated with toxicity or severe side effects. These side effects appear to be dose-related and are less likely to occur at the dose proposed in this study. The most frequently reported side effects are gastrointestinal in nature, including epigastric pain, nausea and vomiting. Other, less frequent side effects include nervousness, headaches, low energy, sweating, joint and muscle pain, blurred vision and insomnia. Hepatotoxicity can occur but typically at much higher doses (e.g., 200-300 mg daily) and resolves when NTX is discontinued. Additionally, case reports have reported elevated liver enzyme tests in patients who were taking non-steroidal anti-inflammatory drugs in combination with high-dose NTX. NTX has been shown to have an effect on the embryo in the rat and the rabbit when given in doses approximately 140 times the human therapeutic dose.

Thus, we will not enroll pregnant or nursing women or those who do not agree to use a reliable form of birth control. NTX, as an opioid antagonist, can block the effects of opioids and can precipitate opioid withdrawal in an opioids dependent individual. Thus, we will not enroll opiate dependent individuals, those requiring opioids for analgesia, and those who have a positive urine toxicology test for opioids.

Before FDA approval, extended release naltrexone was studied in more than 900 patients [63]. Extended release naltrexone appears to be generally well tolerated, and adverse effects tend to be mild [61, 110]. Patients using extended release naltrexone do not develop tolerance for or dependence on the medication.

The extended release formula has been shown to be safe, tolerable, and efficacious in the treatment of alcohol use disorders [61]. In this large 6-month multi-site study in the treatment of alcohol dependence the most common adverse events (AEs) were nausea, headache, and fatigue. Other less common AEs included insomnia, vomiting, decreased appetite, diarrhea, dizziness, injection site pain, nasopharyngitis, and upper respiratory tract infection. Nausea was mild or moderate in 95% of cases; however the large majority of these cases occurred only during the first month of treatment. The most common injection site reaction was tenderness. Seven patients (1%) discontinued injections due to site reactions. Study discontinuation secondary to AEs occurred in 29 (14.1%) of the 380mg naltrexone group, 14(6.7%) of the 190mg group, and 14 (6.7%) in the placebo group. Group differences were accounted for by a greater number of AEs of nausea, injection site reaction, and headache. The percentage of patients who experienced serious AEs (SAEs) was similar among groups (5.4% for 380mg, 4.8% for 190mg, and 7.2% for placebo). The most common SAE was hospitalization for alcohol intoxication. Two SAEs (eosinophilic pneumonia and interstitial pneumonia) were judged as possibly related to study medications. Mean AST and ALT levels did not change significantly over the course of treatment or with medication. A recent large study of extended release NTX found that mean liver enzymes did not change significantly over the course of treatment and there was no effect of medication on the proportion of patients in the different groups who had liver enzyme elevations higher than 3 times the upper limit of normal [61]. In addition, it has been found to be safe for use in patients with mild to moderate liver impairment [109] with evidence of a 15% greater reduction in liver enzyme levels in the NTX group as compared with the placebo group [110].

In a 3-month study of 315 alcohol dependent patients [110] who received monthly injections of NTX, there were no major differences between the NTX group and the placebo group in terms of serious adverse events, adverse events other than injection site reactions, or reactions at the injection site. Six subjects experienced serious adverse events. One subject in the NTX group experienced two such events (i.e., an orbital fracture and a human bite to the face). Five subjects in the placebo group experienced serious adverse events (three subjects were hospitalized due to alcoholic relapse, one of whom required detoxification and had suicidal depression; one subject required surgical repair of an ulnar fracture; and one subject was hospitalized for cellulitis at the injection site, which resolved within 2 weeks). There was no overall group difference in the percentage of patients reporting one or more adverse events. The most common adverse events were headache, nausea, and fatigue. Three adverse events differed significantly by treatment group: upper abdominal pain was more common in the NTX group, and irritability and chest pain occurred more commonly among placebo subjects. Injection site adverse events occurred at an overall frequency of 5% and this rate differed significantly by group. A significantly greater percentage of subjects in the NTX group reported one or more injection site reactions. The most common injection site reactions were pain, induration, and contusion, with a trend for pain to be more common in the NTX group.

While the concern for NTX's hepatotoxicity appropriately warrants monitoring of liver function, theoretically and based on the minimal existing literature on interactions between NTX and HAART, these interactions should be clinically insignificant. Many of the medications used for the treatment of HIV are metabolized via the cytochrome P-450 system (CYP450) leading to issues surrounding drug interactions with a number of medication classes. The metabolism of NTX, however, is not entirely metabolized via CYP450 and therefore significant interactions with HAART medications would not be expected [111, 112]. The first step of NTX metabolism involves hydroxylation which likely involves the CYP450 system. The second step, glucuronidation, does not involve the CYP450 system. These findings would indicate that given the hydroxylation step being CYP450-dependent, it is important to monitor for interactions with the non-nucleoside reverse transcriptase class of HIV medications as well as being vigilant to the fact that patients with impaired hepatic function due to HCV or alcohol dependence. One study evaluating the effect of opioid medications on the disposition of the antiretroviral medication zidovudine (AZT) found that NTX had no significant effect on the area under the curve, maximal concentration or half-life of AZT [113]. In turn, another study suggested that NTX might potentiate the antiviral effects of AZT and one of the protease inhibitors Indinavir, increasing their antiviral activity 2-3 fold [9]. In addition, a large multi-center safety study of the use of NTX for alcoholism in 865 individuals, including patients with comorbid psychiatric illness, concomitant medications, polysubstance abuse, and HIV demonstrated that serious side effects in these populations were uncommon [115]. While this study was not randomized in design and was intended to look at medication interactions, the findings are reassuring for patients with HIV disease. Extended release naltrexone is approved for use in patients who meet criteria for Childs-Pugh A and B liver disease. While these data are reassuring, monitoring of liver function, to assess for hepatotoxicity, will be important, especially in HIV/HCV co-infected patients. The proposed study will systematically examine the question of medication interactions by closely following for adverse effects.

**3. Source:** a) Identify the source of the drug, device or biologic to be used.

Extended release VIVITROL will be provided from Alkermes Inc., Waltham, MA. Injectable placebo will be donated by Alkermes.

b) Is the drug or device provided free of charge?  Yes  No, the medication will be paid for with funding from the grant (NIAAA).

If yes, by whom? VIVITROL will be donated by Alkermes.

**4. Preparation and Use:** Describe the method of preparation, storage, stability information, and for parenteral products, method of sterilization and method of testing sterility and pyrogenicity.

**5. Use of Placebo:**  Not applicable to this research project

Provide a justification which addresses the following:

a. Describe the safety and efficacy of other available therapies (if any).

Other medication options that have been approved for the treatment of alcohol problems by the Food and Drug Administration (FDA) are acamprosate (Campral), and disulfiram (Antabuse). As with NTX and with any other medication, acamprosate, disulfiram, and topiramate (currently not FDA-approved for treatment of alcohol problems) have side effects about which patients should be informed by their physicians. Other non-medication treatments include psychotherapy and referral to Alcoholics Anonymous or other support groups. All three medications and forms of psychotherapy such as cognitive behavioral therapy and

b. State the maximum total length of time a participant may receive placebo while on the study.

24 weeks.

c. Address the greatest potential harm that may come to a participant as a result of not receiving effective therapy (immediate or delayed onset.)

Throughout the study both groups, the naltrexone and the placebo group, will receive psychosocial counseling focused on reducing their heavy drinking. This form of treatment, while not pharmacotherapy, has been shown to be effective therapy for heavy drinking and alcohol abuse and dependence.

d. Describe the procedures that are in place to safeguard participants receiving placebo.

All participants will be informed that there is a chance that they may receive placebo as part of this study. All participants will receive active therapy in the form of psychosocial counseling which will include Medical Management and Medication Coaching which focuses on helping patients take their antiretroviral medication. They will receive this combined counseling treatment during 8 sessions.

